Prior to recruitment the study team will test study feasibility through potential user one-on-one interviews and focus groups to test the usability and language of the app, the information contained within it, the informed consent document and an HIV quiz to ensure these tools are understandable by potential study participants. Additionally, the study team will host a meeting with Wits RHI's HIV-positive Community Advisory Group (CAG) to garner feedback, gauge interest in the app and test usability. This qualitative feedback on app use and interpretation of data will be used to improve the app design and client information. Due to the proof-of-concept nature of the study, we will not conduct a pilot, but we will monitor and review progress regularly, and act on any feedback received from app users.

Recruitment

Study participants will be recruited at HIV clinics after receiving a confirmatory HIV test and following the drawing of CD4 count bloods. A trained and GCP-certified research staff member will approach patients and inform them about the study, and invite them to get pre-screened for participating in the study. The study team is aware this can be a traumatic time for individuals, but previous research has provided RHI staff with useful experience to ensure that the research staff are appropriately sensitive to the patient's feelings and needs. The recruitment site will be organised for efficient flow of potential participants which will include a private space for consenting to the study, collecting patient information and app installation/training. Two recruiters will work at each site, minimising the waiting time for potential participants.

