Upon signing informed consent, their personal details including name, surname, ID number, and a baseline survey which consists of a HIV/CD4 count knowledge questionnaire (all tools listed in appendix II) will be recorded into REDCap (Harris et al, 2009), an electronic data capture tool hosted at Wits University², using a tablet device by trained research staff. At the end of the recruitment process all patients will be provided their R50 participation allowance. Patients in both study arms will be encouraged to return to the clinic as per the clinic guidelines to receive their CD4 result and attend wellness or HIV care follow-up.

REDCap will randomise the participant to the standard of care or intervention arm through the device without informing the participant. Participants randomised to the standard of care arm will be provided with a copy of their signed informed consent document and thanked for their time.

Participants randomised to the intervention arm will be told about the smartphone app and told how it works. The study staff member will install the app on the participant's phone and assist the participant in setting up an account with a username, password and PIN number and provide an overview of how the app and notification system works. Participants will be

² REDCap (Research Electronic Data Capture) is a secure, web-based application designed to support data capture for research studies, providing: 1) an intuitive interface for validated data entry; 2) audit trails for tracking data manipulation and export procedures; 3) automated export procedures for seamless data downloads to common statistical packages; and 4) procedures for importing data from external sources.

informed that they are welcome to use the app at any time, and it will notify them when a laboratory result has arrived. As mentioned above, the cost per laboratory result received is approximately R0.02. Patients will be informed of this cost prior to participating.

[figure not shown]

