The aim of the study is to show that smartphone apps work for that proportion of the population that currently have Android smartphones, not that it works for the general population. Smartphone purchase is rapidly increasing in South Africa, with 75% of new cell phones sold in South Africa currently being smart phones. We expect that randomization and a large sample size will enable us to have a reasonable balance between the arms, unless participants randomized to the control group request study withdrawal due to not getting the app.

Sample Size

Based on a primary endpoint of a second HIV-linked laboratory test (CD4, viral load) being performed at a clinical facility, within 8 months after the HIV-positive result, suggesting successful attendance and entry into HIV care, we anticipate at least 1000 patients in each arm will be needed. The study team expects to see a 20% difference in linkage to care levels through the app (using a second HIV-linked laboratory test as an indicator for linkage to care). The sample size is calculated based on 80% power, 0.05 significance with a loss-to-follow-up rate of approximately 27% (Hillbrow CHC data). Both ART and pre-ART patients will be expected to return for a follow-up laboratory test around 6 months after diagnosis; ART patients for a viral load, and pre-ART for a follow-up CD4 count.

In South Africa, both younger and male clients have lower linkage to care rates than females and individuals over 25. In order to conduct subgroup analysis on these higher-risk populations (young people and men), there will be an over-sampling of male patients and those between the ages of 18 (the age of majority) and 25 for both the intervention and control arms given that it has been shown that these groups are less likely to access health services efficiently (Kranzer, 2010). These populations will be recruited until 250 of these individuals are included in both arms to ensure the study is powered to analyse the effect in these key subgroups. Based on a 20% difference in linkage to care for the intervention/app arm with an 80% power, a significance level of 0.05 and a loss-to-follow-up rate of 40% a sample size of 97 per arm is required. Again, the study team will over-sample based on the proof-of-concept nature of the study.

Figure 2: *Recruitment flow chart*

App specifications

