Should a participant have any issues regarding their diagnosis or the study they will be able to access help. At recruitment they will be told that for HIV-related queries they can call the HIV/AIDS helpline numbers that are shown in the app. For study-related queries, they can call the study team on the phone numbers that are listed in the study documentation.

Data management & statistical analysis

Data management

Patient recruitment, demographic, baseline and follow-up survey data will be collected by a trained and GCP certified researcher using a mobile device (tablet) connected to the REDCap database. REDCap is a secure web-based application designed for virtually collecting clinical research data and is used by over 150,000 projects around the world (more information at: <http://project-redcap.org/>). The REDCap Android app, which will be installed on the tablets, allows for off-line data collection if there is no internet connection available.

Laboratory results will be added to the NHLS laboratory database as they are received and pushed to the participant through an application layer that is part of the smartphone app. The REDCap database will be connected to the NHLS laboratory database using an API (application programming interface). All HIV-related NHLS laboratory results will be recorded as part of the study to monitor the total number and frequency of laboratory tests on study participants. All data transmission between electronic databases/servers will be secured and encrypted.

Paper records (completed informed consent) will be in the control of study staff for the day they are collected. At the end of each day they will be returned to a centralised location (e.g.: RHI offices) where they will be scanned and archived in a data storage room. Once archived the paper records will only be accessed under special circumstances (e.g.: a patient withdraws or a confirmation of a patient's acceptance to be in the study is required).

Data analysis will be conducted by research staff with all identifying participant data de-identified.

Analysis plan

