Appendix III: App specifications

General use case description:

- I. A newly diagnosed HIV-positive patient with Android smartphone will be enrolled to the SmartLtC study by study staff and randomised to receive the smartphone app or not. Upon being randomised to smartphone app arm, the study staff member will install the app on the phone through a USB cable connection, (or through a Library Box - <http://librarybox.us/whatis.php>). The app icon and name will not refer to health or medicine in any way to ensure privacy for the user.
- II. Once app has been installed patient will create username and password, and select PIN code. The app can then be accessed immediately which will provide access to “More information” and “FAQ’s” (Frequently Asked Questions)⁵ sections, but will not include lab results. The study staff member will provide the patient with a brief training session on use of the app. Patients will be informed that they can read “More information” and “FAQ” sections at any time, but laboratory results will only be displayed after they have been received. All past results will be accessible to the patients and displayed along with any new results.
- III. When a CD4 count/Viral Load (VL) result is received by the NHLS database an App-based notification will show on the patient's screen informing them new information is available and to open the app. (Suggested text for the app-based notification “You have new information waiting. Please open the app”.) Once the patient opens the app and enter their PIN code (which is verified by the server) their CD4/VL result is shown under “Lab results” in the app. The CD4 count/VL results will be written in red, yellow or green to highlight the relative immediacy of action needed by the patient.
- IV. If the patient selects a CD4 count number (to be a suggested action on screen), a pop-up screen will provide a basic explanation of what that CD4 count means and what action they need to take. (Note: The numerical text will be coloured and the pop-up screen will also display a visual-analogue scale going from red to yellow to green, with a marker showing where the patient's CD4 count sits along the scale.) At the bottom of the pop-up will be a link to more detailed information about HIV and laboratory results. On every screen will be a link to a help page which displays the contact number for the National AIDS Helpline and the study coordinator.

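### The safety section's only named route for HIV-related questions runs through the app, so as written it does not reach the control arm

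*Protocol*

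**What the plan says.** The Safety considerations section of the protocol makes a general promise: "Should a participant have any issues regarding their diagnosis or the study they will be able to access help". It then splits the help into two routes. For the virus and the diagnosis, participants are to hear at recruitment that "for HIV-related queries they can call the HIV/AIDS helpline numbers that are shown in the app". For the study itself, "they can call the study team on the phone numbers that are listed in the study documentation".

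The Recruitment section sets out what each arm leaves with. "Participants randomised to the standard of care arm will be provided with a copy of their signed informed consent document" and are thanked. By contrast, "Participants randomised to the intervention arm will be told about the smartphone app and told how it works", and staff then install it for them. Appendix III describes patients as "randomised to receive the smartphone app or not". The paragraph before Sample Size foresees that participants in the "control group request study withdrawal due to not getting the app".

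On the moment of recruitment, shortly after a confirmatory positive test, the Recruitment section says: "The study team is aware this can be a traumatic time for individuals". It adds that research staff have relevant experience in handling this sensitively.

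**The concern.** The promise of help covers everyone in the trial, but the route named for HIV-related questions depends on an item that is allocated by randomisation. A recruiter who followed the safety section word for word would direct a newly diagnosed control participant to a screen which that person does not have. The section also separates the two places where numbers are found, with study-team numbers in the documentation and helpline numbers in the app, so it does not suggest that the helpline number is on paper too.

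At stake is a participant-protection provision at a point which the protocol itself recognises as difficult. The stated safety route should work for all the people it is said to cover.

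**Working it through.** The plan gives no figure on this point, so the check sets the relevant texts side by side.

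1. **Who is promised help?** Safety considerations speaks of a participant, with no arm named. The promise therefore covers controls.
2. **Where is the helpline number, according to that section?** In the app. No second location is given.
3. **Who has the app?** Recruitment installs and explains it for the intervention arm only. Appendix III and the remark before Sample Size about control participants withdrawing both confirm that controls go without it. No later offer of the app to controls is described.
4. **Is the helpline number placed anywhere else?** The other mentions are in the footnote to App specifications on how results are displayed, and in the use-case description and requirements table of Appendix III. All of them place the number inside the app.
5. **What other contact do controls have?** Intervention lets participants give the team feedback by phone or SMS at any time. Participant opt-out gives everyone the study team's contact details. Safety considerations puts the team's numbers in the study documentation. So the study-team route reaches both arms, but the safety section assigns it to study questions.
6. **What cannot be checked?** The consent form (Appendix I), of which controls keep a copy, was not available. It may list the helpline.

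Steps 1 to 3 give the result: the promise covers both arms and the named route for HIV questions covers one. Steps 4 and 5 show that no other text available for review repairs this. Step 6 limits what can be concluded.

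**Number of people concerned.** Sample Size plans at least 1000 per arm, hence at least 1000 controls. SAP section 5 expects about 350 in total. If allocation is equal, 350 × 1/2 = 175 controls. The protocol plans equal arms, but the SAP does not state the ratio. Both figures count people without the app. They do not count people without the helpline number, which cannot be known from these documents.

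**The case against.** The strongest reply is that the consent form is the natural place for a helpline number, that controls take a copy home, and that its absence from this review is not a gap in the plan. That stands, and it rules out any statement that controls never receive the number. It does not rescue the safety section's wording, which names the app as the place for the helpline and the documentation as the place for the study team. If the form does list the helpline, the section should say so.

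A second reply is that the helpline is a national service and that participants are to be told of it at recruitment, so controls are not barred from calling. This also stands. The gap is that the text does not say where a control participant finds the number.

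Three stronger readings are tempting, and the documents support none of them.

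- *Controls are left without support.* They have the study team's numbers, they are recruited inside HIV clinics by staff prepared for the situation, and both arms are encouraged to return for results and care.
- *App users who withdraw and have their account deleted also lose the number.* The requirements table in Appendix III places the help icon on every screen, including login, and Participant opt-out does not say that the app is removed. As specified, the number does not depend on an active account.
- *The helpline confounds the comparison, because a difference in linkage might come from the number and not from results and reminders.* The primary objective compares access to the app with standard of care. The help page is a specified part of the app, so any effect of it belongs to the effect being estimated.

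**Conclusion.** The point holds as a gap in arm coverage in the safety text: the route named for HIV-related questions does not, as written, reach the control arm, although study-team contacts do. It concerns all controls, at least 1000 at the protocol's size or about 175 at the SAP's size under equal allocation. It rests on the text available for review and is conditional on the unseen consent form: if the form carries the number, only the wording needs correcting; if it does not, the number must also be supplied.

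Nothing here touches the sample size, the error rates, the primary analysis or the validity of the linkage comparison. It is a modest correction, worth making because it concerns participant protection and costs almost nothing.

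**What to change.** Reword Safety considerations along these lines: at recruitment, every participant in both arms is given the national HIV/AIDS helpline number and the study-team number in writing, for example on the copy of the consent form; the same numbers are also shown in the app.

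Then check the consent form. If the helpline number is missing, add it and supply it to controls already enrolled. SAP section 4.3 describes randomisation in the past tense, so there may be some. The recruitment survey in Appendix II collects phone numbers, so they can be reached. The protocol's own background section regards SMS as not private, which should guide how the number is passed on. Because this would be an extra contact in one arm, possibly within the 8-month linkage window, keep it to the number itself and record its date.

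The cost is one line on a document already handed out. Display of the helpline would no longer be unique to the app, which should narrow the contrast negligibly if at all. A REDCap item confirming that the numbers were given is optional.
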